NCT04626947

Title: Prevention of Recurrent Clostridium Difficile Infection (CDI) in Patients With Inflammatory Bowel Disease (IBD)

Protocol: Version 1. 10/25/2019

Study Title: Prevention of recurrent Clostridium difficile infection (CDI) in patients with inflammatory bowel disease (IBD)

Institution Name: University of Pittsburgh School of Medicine

Principal Investigator: [name], AGAF, FACG

Professor of Medicine, Clinical and Translational Science

Co-Director, UPMC Inflammatory Bowel Disease Center

Director, Translational Inflammatory Bowel Disease Research

Director, Nutrition Support Service

Division of Gastroenterology, Hepatology and Nutrition

Department of Medicine. University of Pittsburgh School of Medicine

Investigator Contact Information: [name]

[contact] [contact]

1. Objectives & Hypotheses

- a. Primary objective: Compare the short term tolerability and effectiveness of enhanced CDI therapy with Bezlotoxumab in patients with IBD after CDI. Special attention will be paid to rates of recurrent CDI, healthcare utilization, quality of life and disease activity.
- b. Secondary objective:
Evaluate the long term clinical outcomes of enhanced CDI therapy with Bezlotoxumab in patients with IBD. 90 days, 1 year and 2 year patterns of recurrent CDI, healthcare utilization, quality of life and disease activity will be assessed. We will use our published control population as well as patients who agree to be monitored but do not receive enhanced therapy as the control population.

Hypothesis: Administration of a human monoclonal antibody that binds to Clostridium difficile toxin B (Bezlotoxumab) in IBD patients with documented CDI will safely and effectively improved long-term clinical outcomes assessed by reduced rates of recurrent CDI, healthcare utilization, quality of life and disease activity and reduced overall charges associated with two year patterns of care.

2. Background & Rationale, Significance of Selected Topic & Preliminary Data

Inflammatory bowel diseases, including Crohn's disease and ulcerative colitis are lifelong chronic inflammatory conditions characterized by multiple remitting and relapsing events. During their lifetime, patients will experience multiple hospitalizations and surgical interventions as a part of the natural course of their disease. IBD patients frequently require corticosteroids, immunomodulators and biologic agents to induce and

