This is a prospective, single center, non-randomized, observational, open label study to compare tolerability, efficacy, and short and long term clinical outcomes of Bezlotoxumab in CDI IBD patients.

A total number of 50 patients will be enrolled. Patients who agreed to receive Bezlotoxumab will be compared to our recently published historical controls as well as IBD registry patients who do not elect to receive enhanced *C difficile* therapy.

Patient population will include any patient who receives care at the Digestive Disorder Center at UPMC Presbyterian Hospital.

Inclusion criteria: >18 years old, diagnosis of IBD and CDI.

Exclusion criteria: <18 years old, no IBD, no CDI, history of colectomy.

4. Study Flowchart

Data collection:

Visit 1 (Enrollment)

- a. Demographic information
- b. type of IBD
- c. disease duration
- d. history of bowel resection
- e. current medications
- f. inflammatory markers: CRP, ESR, Albumin
- g. CBC
- h. quantitative immunoglobulins
- i. Vitamin levels (Vit D and Vit B)
- j. Disease related quality of life (SIBDQ)
- k. Disease activity scores (HBI-UCAI)
- l. Dietary intake (sugar and fat intake)

m. Stool sample

Visit 2 (90 days after enrollment)

Clinic visit or Telephone call

- a. inflammatory markers: CRP, ESR, Albumin (if available as a standard of care)
- b. CBC (if available as a standard of care)
- c. Disease related quality of life (SIBDQ)
- d. Disease activity scores (HBI-UCAI)
- e. ED visits
- f. Hospital admissions

Visit 3 (1 year after enrollment)

Clinic visit or Telephone call

- a. inflammatory markers: CRP, ESR, Albumin (if available as a standard of care)
- b. CBC (if available as a standard of care)
- c. Disease related quality of life (SIBDQ)
- d. Disease activity scores (HBI-UCAI)
- e. ED visits
- f. Hospital admissions

Visit 4 (24 months after enrollment)

Clinic visit or Telephone call

- a. inflammatory markers: CRP, ESR, Albumin (if available as a standard of care)
- b. CBC (if available as a standard of care)
- c. Disease related quality of life (SIBDQ)
- d. Disease activity scores (HBI-UCAI)
- e. ED visits
- f. Hospital admissions
- g. Total charges associated with cost of care

5. Study Procedures:

This is a prospective observational study comparing the effectiveness of Bezlotoxumab to reduce rates of CDI in patients with IBD. We will evaluate short and long-term clinical outcomes after treatment with Bezlotoxumab.

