In the primary analysis, we will compare the risk of recurrent CDI between the 50 treated and 118 controls at 90 days after enrollment. The inverse propensity score-weighted method will be used to estimate the proportion of recurrence CDI at 90 days under Bezlotoxumab among IBD CDI patients seen in the clinics and compared with that for IBD CDI patients without Bezlotoxumab. Other long-term outcomes for comparison include, number of healthcare utilization (emergency room visits and hospitalization), overall charges during the second year after the study enrollment; inflammatory markers and CBC (in continuum and binary: abnormal vs normal), SIBDQ, HBI-UCAI, dietary intake at the 90 days, 12-month and 24-month visits. The inverse probability-weighted method will be used to compare these outcomes between Bezlotoxumab-treated and controls with IBD CDI. Cardiac failure will be closely monitored throughout this study and the proportions of cardiac failure among the 50-treated patients by the first 90 days, 12 months and 24 months will be estimated. The paired t-test or the nonparametric signed-rank test will be used to test the change baseline to the 24-month visit in continuous outcomes and the McNemar test will be used to for discrete outcomes.(9)

Using data from the 50 IBD CDI patients, linear-mixed models and generalized linear-mixed models will be used to explore the longitudinal change in the repeatedly measured assessments of disease activity and quality of life, including current medications, inflammatory markers, annual overall financial charges, annual use of healthcare facilities (such as emergency room visit and number of hospitalizations) SIBDQ, and HBI-UCAI. Trajectory analyses on these multiple longitudinal patient outcomes will be used to identify IBD CDI patients who have responded to the treatment and who have not. Subsequently we will compare the baseline patient characteristics between the treatment responders and non-responders and the results will be invaluable in guiding future management of IBD CDI patients.

Based on data from 28 IBD CDI patients, it was reported that the proportion of IBD patients with recurrent CDI within 12 weeks of follow-up was 26.7% among Bezlotoxumab-treated and 53.8% among those without Bezlotoxumab (10-11). With 118 controls and 50 Bezlotoxumab-treated patients, we will have 88% power to detect the same difference by using the Fisher's Exact test with a 2-sided alpha level at 0.05.

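### Follow-up dietary intake and repeated current medications are planned for analysis in Section 7, but Section 4 schedules both at enrollment only, and no follow-up source is stated for either

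*Combined protocol and SAP*

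**What the plan says.** Section 7 (Statistical Analysis and Sample Size Justification) uses the two variables in different ways.

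- **Diet** is a between-group outcome. The list of longer-term outcomes ends with "dietary intake at the 90 days, 12-month and 24-month visits", and the next sentence gives the method: "The inverse probability-weighted method will be used to compare these outcomes between Bezlotoxumab-treated and controls with IBD CDI".
- **Medications** are a within-group, exploratory outcome, modelled in the 50 treated patients only. There, "linear-mixed models and generalized linear-mixed models will be used to explore the longitudinal change in the repeatedly measured assessments"; the first measure that the sentence goes on to name is the patient's current drugs. The same set of longitudinal outcomes then feeds a trajectory analysis meant to tell treatment responders from non-responders.

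Section 4 (Study Flowchart) lists "e. current medications" under Visit 1, and item l of the same visit begins "Dietary intake (sugar and fat intake". Neither item appears under Visits 2, 3 or 4. Those visits list inflammatory markers and CBC (if available from routine care), SIBDQ, HBI-UCAI, emergency visits and admissions. Visit 4 adds total charges.

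**The concern.** A single enrollment value cannot supply a follow-up comparison or a longitudinal model. If the visit lists are followed as they stand, the diet comparison has nothing to compare at any of its three time points. The medication model has one value per patient, from which no change can be estimated, and the responder analysis loses one of its named inputs.

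Medications also matter for describing the results. Section 2 says that "IBD patients frequently require corticosteroids, immunomodulators and biologic agents to induce and" maintain remission, that CDI often sets off a flare, and that antibiotics were still needed in the year after infection in the group's earlier cohort. Changes in therapy over two years are therefore to be expected. A reader of the 24-month HBI-UCAI and SIBDQ results will want to know what treatment patients were on by then. Diet not asked about at a visit is unlikely to be recoverable later, so the question is best settled before follow-up contacts take place.

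**Working it through.** This is a comparison of two sections, and the only arithmetic in the point itself is a count.

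**Step 1. Schedule against analysis.**

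| Item | Visit 1 | Visit 2 (90 days) | Visit 3 (1 year) | Visit 4 (24 months) | What Section 7 needs |
|---|---|---|---|---|---|
| Dietary intake | yes | no | no | no | values at 90 days, 12 and 24 months, both groups |
| Current medications | yes | no | no | no | repeated values, 50 treated patients |
| SIBDQ, HBI-UCAI (for contrast) | yes | yes | yes | yes | repeated values |

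Diet: 1 of 4 visits, so 1 − 1 = 0 of 3 follow-up visits. Medications: the same, 0 of 3.

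**Step 2. What each analysis can estimate from one enrollment value.**

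- Weighted group comparison at a follow-up visit: needs a value at that visit. None is scheduled for diet.
- Mixed-model change over time: needs at least two time points in the data. Only one is scheduled for medications.
- Baseline to 24-month change (paired t, signed-rank or McNemar test): needs a 24-month value. None is scheduled for either item.

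**Step 3. Other possible sources.** Apart from the flowchart and the follow-up analyses, medications appear in Section 7 only as a baseline characteristic. Section 5 recruits from the IBD Registry, and the title of reference 6 describes a registry derived from electronic health record data. Medications could plausibly be drawn from it, although no sentence says they will be. Nothing in the document points to a follow-up source for diet.

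**Step 4. The plan's own figure, to confirm that it is not involved.** Section 7 gives 88% power for recurrence of 26.7% (n = 50) against 53.8% (n = 118), two-sided alpha 0.05.

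- Pooled proportion: (50 × 0.267 + 118 × 0.538) / 168 = 0.457.
- Standard error under the null: √[0.457 × 0.543 × (1/50 + 1/118)] = 0.0841.
- Standard error under the alternative: √[0.267 × 0.733/50 + 0.538 × 0.462/118] = 0.0776.
- Continuity correction: 0.5 × (1/50 + 1/118) = 0.0142.
- Power: Φ[(0.271 − 0.0142 − 1.96 × 0.0841) / 0.0776] = Φ(1.19) = 88.2%.

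This reproduces the stated figure. Full enumeration of Fisher's exact test gives 90.0%. Neither diet nor medications enters the calculation.

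**The case against.** The strongest reply is that the visit lists are not exhaustive. They also omit recurrent CDI, which is the primary outcome, and cardiac failure, although Section 7 plans to estimate both. Absence from the flowchart is therefore weak evidence that an item will not be collected. Section 2 also says that the study will reuse the structure of the group's earlier work, which reported antibiotic use after infection, so drug data after infection were obtainable for that cohort. This stands for medications: the supportable statement is that the source is unspecified. It does not rescue diet, for which no follow-up source is given.

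A second reply concerns the controls. Adding dietary questions to later visits would not produce the comparison with all controls, because the published historical controls cannot be asked. This stands, and it shapes the fix.

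A reader might go further and infer that, without follow-up medications, the two-year disease activity comparison is confounded by changes in IBD therapy, so that a benefit could be hidden or created. The documents do not support that as a fault in the plan. Therapy changes come after treatment and may be among its effects; fewer escalations could be part of a benefit. Comparing HBI-UCAI and SIBDQ whatever therapy followed is a legitimate question, and Section 7 does not claim to isolate an effect free of later therapy. The documents give no escalation rates or effect of escalation from which to size a bias. Recording medications would describe therapy changes but would not by itself separate their effect.

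**Conclusion.** The contradiction between Sections 4 and 7 is real and should be reconciled. For diet, the planned weighted comparison at 90 days, 12 months and 24 months has no scheduled data at any of the three time points and cannot be run as written. For medications, the planned longitudinal model in the 50 treated patients has no stated source beyond enrollment; whether it can be run depends on registry data that the protocol does not mention.

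The effect is confined to secondary and exploratory analyses. The conclusion rests on reading the visit lists as the only stated collection plan for these two items. It does not show that follow-up medications will go unrecorded, nor that the disease activity and quality of life comparisons are invalid.

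**What to change.** **Medications.** In Section 4, add current medications, with changes since the last contact, to Visits 2, 3 and 4 for treated patients and concurrent controls. State whether they come from the visit, the telephone call or the registry. Section 7 models them only in treated patients; recording them in concurrent controls as well lets therapy changes be described for both groups alongside HBI-UCAI and SIBDQ.

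**Diet.** Choose one of two options:

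1. Add the Visit 1 dietary questions to Visits 2, 3 and 4, and state in Section 7 that the follow-up diet comparison is restricted to treated patients and concurrent controls.
2. Delete dietary intake from the follow-up outcomes in Section 7 and keep it as a baseline characteristic.

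**Cost.** Protocol wording, a few data fields, and a few minutes at each of the three follow-up contacts already planned. Option 1 also gives a smaller diet comparison. Its size cannot be stated, because the document does not split the 118 controls into historical and concurrent patients. Option 2 gives up a secondary outcome and adds no work.

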Patients who are part of the IBD Registry and have a defined IBD diagnosis and CDI will be approached to be consented for this study. Randomly the study treatment will be offered to 50 patients.

Diagnosis of CDI will be accomplished using the standard CLIA certified strategies employed in our microbiology/virology clinical laboratories, which include PCR amplification, two step GDH /gene amplification of liquid/unformed stool samples.

Patients will be divided into 2 groups of treatment and followed in a parallel fashion for the next 2 years: 1. Those who agree to receive Bezlotoxumab (Case) and 2. Those who do not agree to received Bezlotoxumab (controls).

6. Study Duration:

Total duration time: 5 years. 36 months enrollment and 24 months follow up.

7. Statistical Analysis and Sample Size Justification:

Sample size: 50 (Based on the prevalence of CDI within our patient population)

Descriptive statistics of baseline characteristics will be used to characterize the 50 IBD CDI patients who agree to receive Bezlotoxumab. The baseline characteristics under consideration include demographic data, type of IBD, duration of IBD, current medications, inflammatory markers, SIBDQ, HBI-UCAI and others collected at the time of enrollment. Mean, standard deviation, median and interquartile range will be reported on continuous variables and proportions reported on discrete variables.

Similar baseline characteristics will be collected at enrollment among historical controls and IBD registry patients who do not elect/ not offered to receive enhanced C difficile therapy. Similar descriptive statistics will be used to characterize these controls. A logistic regression model will be developed to predict the status of receiving Bezlotoxumab from the extensive list of baseline characteristics. Subsequently each study participant, including both the 50 patients who receive Bezlotoxumab and the controls, will be assigned a predicted probability of treatment based on this propensity score model. The inverse probability weighting method will be used to compare the Bezlotoxumab-treated IBD CDI patients and the controls in baseline characteristics to demonstrate balanced baseline characteristics between the two groups after inverse probability weighting (8).

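### SIBDQ, HBI-UCAI and laboratory comparisons use each patient's baseline value only through the propensity weights; adding it to a two-group outcome model gains precision and guards against baseline-related loss.

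*Combined protocol and SAP*

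**What the plan says.** Section 7 (Statistical Analysis and Sample Size Justification) builds the weights first: "A logistic regression model will be developed to predict the status of receiving Bezlotoxumab from the extensive list of baseline characteristics". The baseline list includes "inflammatory markers, SIBDQ, HBI-UCAI and others collected at the time of enrollment", so three of the outcome families are named as candidate covariates; CBC, taken at Visit 1, comes in only under the general term. The plan intends the same information for controls: "Similar baseline characteristics will be collected at enrollment among historical controls and IBD registry patients". It will also check that the weighted groups are balanced at baseline.

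The later outcomes include "SIBDQ, HBI-UCAI, dietary intake at the 90 days, 12-month and 24-month visits", along with inflammatory markers and CBC, the last two both as continuous values and as abnormal versus normal. The only method named for the group comparison is this: "The inverse probability-weighted method will be used to compare these outcomes between Bezlotoxumab-treated and controls with IBD CDI".

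Two other analyses use baseline or repeated values, but neither compares the groups. One is within-patient change: "The paired t-test or the nonparametric signed-rank test will be used to test the change baseline to the 24-month visit in continuous outcomes". The other is longitudinal: "Using data from the 50 IBD CDI patients, linear-mixed models and generalized linear-mixed models will be used to explore the longitudinal change".

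Section 4 (Study Flowchart) lists follow-up laboratory values conditionally: "inflammatory markers: CRP, ESR, Albumin (if available as a standard of care"; CBC carries the same condition. The documents give no expected loss rate, no missing-data method and no weights for loss to follow-up.

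**The concern.** The baseline value of the same measure is usually among the strongest predictors of its follow-up value. Using it only in the propensity model has two consequences.

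- **Precision.** With 50 treated and 118 controls, weighting leaves some chance imbalance in that value, and the outcome variation it explains stays in the error term.
- **Missing follow-up.** Section 7 assigns a propensity score to every participant. Weights that balance everyone enrolled need not balance those still observed at 12 or 24 months.

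These comparisons carry the quality-of-life and disease-activity parts of both objectives in Section 1.

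**Working it through.** **1. The plan's own figure.** The only power statement concerns 90-day recurrence: 118 controls at 53.8%, 50 treated at 26.7%, Fisher's exact test, two-sided 0.05, power 88%.

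- Continuity-corrected normal formula: d = 0.538 − 0.267 = 0.271; pooled p = (118 × 0.538 + 50 × 0.267)/168 = 0.457; null SE = √(0.457 × 0.543 × (1/118 + 1/50)) = 0.0841; alternative SE = √(0.538 × 0.462/118 + 0.267 × 0.733/50) = 0.0776; correction = 0.5 × (1/118 + 1/50) = 0.0142.
- Power = Φ[(0.271 − 0.0142 − 1.96 × 0.0841)/0.0776] = 88.2%.
- Exact enumeration gives 88.4% with 0.025 in the relevant tail, and 90.0% with the minimum-likelihood two-sided p-value.

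The figure reproduces, but it says nothing about SIBDQ, HBI-UCAI or laboratory values, for which no power is given.

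**2. Textbook gain, for reference only.** Detectable difference at 80% power, ignoring baseline: (1.96 + 0.842) × √(1/118 + 1/50) = 0.473 SD. Multiplying by √(1 − ρ²) gives 0.451, 0.409 and 0.338 SD at ρ = 0.3, 0.5 and 0.7. This overstates the gain here, because the planned weights already use baseline.

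**3. Planned comparison, complete data.** Simulation with assumed inputs: N = 168, about 50 treated; standard normal baseline B; treatment probability logistic(−0.9 + 0.5B); outcome ρB + √(1 − ρ²) × noise; no drug effect. Plain weighting is compared with weighted regression on group and B. Unweighted bias is 0.14, 0.24 and 0.33 SD at the three correlations; weighted bias is about 0. Extra patients = (SE ratio)² − 1.

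| ρ | SE, weights only | SE, baseline added | Worth in patients |
|---|---|---|---|
| 0.3 | 0.172 | 0.170 | (0.172/0.170)² − 1 = 2% |
| 0.5 | 0.161 | 0.157 | (0.161/0.157)² − 1 = 5% |
| 0.7 | 0.138 | 0.129 | (0.138/0.129)² − 1 = 14% |

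That has one covariate. With 6 or 12 propensity covariates and moderate or strong selection, separate sets of runs gave 7-30% and 6-24% at ρ = 0.5, and 2-17% over ρ = 0.3 to 0.5. The top of the range, about 47-54%, needs ρ = 0.7 with strong selection. A baseline imbalance above 0.1 SD remained in about 10-47% of data sets when the propensity model was fitted once and not revised.

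**4. Loss that depends on baseline.** Same set-up as step 3, with probability of being observed logistic(0.95 + sB), s = 0.7 in treated patients, and overall loss about 27-30%. With 2,500 replicates and an SD of about 0.19, Monte Carlo error in the bias is 0.19/√2500 = 0.004.

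| s in controls | Bias of weights only, ρ = 0.3 / 0.5 / 0.7 | Baseline added |
|---|---|---|
| 0.7 (same pattern) | about 0 | about 0 |
| 0 (treated only) | 0.06 / 0.10 / 0.14 SD | within 0.01 SD |
| −0.7 (opposite) | 0.11 / 0.19 / 0.27 SD | within 0.01 SD |

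At ρ = 0.5 the bias is half to one standard error of the estimate: 0.096/0.194 = 0.5 and 0.192/0.189 = 1.0. With 15% loss in treated patients and about 30% in controls, only control loss being tied to baseline, the bias of weighting alone was 0.07-0.19 SD, against about 0.01 SD or less with baseline added. Refitting the weights among observed patients also cut the bias, to about 0.02 SD.

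**5. Loss that depends on the follow-up value itself.** In the treated-only pattern, bias of 0.19-0.20 SD falls only to 0.17 / 0.14 / 0.10 SD. In the opposite pattern, 0.38-0.39 SD falls to 0.35 / 0.30 / 0.20 SD. Baseline adjustment does not cure this.

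**The case against.** A reader might infer that the plan makes no adjustment for baseline. It does: SIBDQ, HBI-UCAI and inflammatory markers are candidate propensity covariates, and a balance check follows. With complete data that is enough for validity, and the remaining loss of precision is modest at ordinary correlations. This part of the objection stands. The plan does not, however, say what happens if balance fails, nor that every outcome's baseline value stays in a model still to be developed.

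It can also be said that the named method is broad: weighted regression with a baseline term, or weights refitted at each visit, would fit the wording. That is true, but the plan commits to neither, and the analyses that do use baseline or repeated values leave out the group comparison.

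A further tempting inference is that two-year loss does bias these results. The documents do not support it. They give no rate or pattern, follow-up may be by telephone, and some controls are already-published historical patients. Bias was about nil when the same loss pattern held in both groups, although in one set of runs unequal rates with the same slope left 0.04-0.10 SD.

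Finally, the simulations tested weighted regression at a single visit, not the repeated-measures model proposed below. That limit stands.

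**Conclusion.** The point holds as an improvement in precision and robustness, not as an error that invalidates the comparison. With complete follow-up, adding baseline is worth roughly 2-30% more patients at assumed correlations of 0.3 to 0.5. With baseline-related loss that differs between groups, weighting alone can be off by about 0.06-0.27 SD, and the baseline term brings this to about zero. Correlations, selection strength and loss patterns are all assumptions.

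It would go too far to conclude that the baseline term deals with missing data in general. Whether a follow-up CRP, ESR, albumin or CBC exists depends on routine care, so it plausibly depends on how ill the patient is at the time, and step 5 shows that much of that bias would remain. Whether baseline values exist for all historical controls cannot be checked from the documents.

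**What to change.** In Section 7:

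- State that the baseline value of each outcome is kept in the propensity model.
- For SIBDQ, HBI-UCAI, CRP, ESR, albumin and CBC, fit one propensity-weighted outcome model to treated patients and controls together, with group, visit, group by visit and the baseline value of the same measure. Use a logistic version for the abnormal/normal laboratory outcomes.
- Use robust or bootstrap standard errors and report the group difference at 90 days, 12 and 24 months.
- State that this removes bias only from loss explained by recorded baseline values.
- Label the laboratory comparisons as subject to outcome-dependent missingness, and add a sensitivity analysis for it.

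The cost is SAP wording and some programming; no new data are needed. The downside is that patients without a baseline value, possibly including some historical controls, need handling, but the propensity model already requires the same.

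### The plan sets out to compare tolerability, but compares no adverse-event outcome between groups: cardiac failure is estimated in treated patients only, with no baseline status recorded

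*Combined protocol and SAP*

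**What the plan says.** All references are to the combined protocol and SAP.

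- **Objective (section 1).** The primary objective is to "Compare the short term tolerability and effectiveness of enhanced CDI therapy with Bezlotoxumab in patients with IBD after CDI".
- **Design (section 3).** The study is described as an "observational, open label study to compare tolerability, efficacy, and short and long term clinical outcomes of Bezlotoxumab in CDI IBD patients".
- **Cardiac failure (section 7).** Close monitoring of this event is promised for the whole study. The analysis planned for it is that "the proportions of cardiac failure among the 50-treated patients by the first 90 days, 12 months and 24 months will be estimated". No definition, data source or control-group count is given.
- **Between-group comparisons (section 7).** Recurrent CDI at 90 days is primary. "Other long-term outcomes for comparison include, number of healthcare utilization (emergency room visits and hospitalization"; the list goes on to charges, inflammatory markers, blood count, quality of life, disease activity and diet. It contains no cardiac failure, adverse event or serious adverse event.
- **Baseline data (sections 4 and 7).** Visit 1 has items a to m, none of them cardiac history or comorbidity. Section 7 says "The baseline characteristics under consideration include demographic data, type of IBD, duration of IBD, current medications, inflammatory markers" and continues with the two scores and an open-ended reference to other enrollment data.
- **Follow-up data (section 4).** Visits 2 to 4 may be telephone calls. They list ED visits and admissions but no cardiac item.
- **Eligibility (section 3).** "Exclusion criteria: <18 years old, no IBD, no CDI, history of colectomy". Prior cardiac failure is not mentioned.
- **Serious events (section 9).** These are reported whatever their cause, to the investigator and the IRB. No tabulation by group is described.
- **Comparator (section 5).** Patients who decline the drug are followed alongside the treated patients for two years.

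**The concern.** A comparison of tolerability needs the same harm outcome, ascertained the same way, in both groups. The plan singles out one harm for close monitoring and then counts it in one group. The documents give no background rate of cardiac failure in this population, so a treated-only proportion has nothing to be read against, although an untreated group is already being followed.

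The second difficulty is the meaning of the count. A cumulative proportion by 90 days, 12 months and 24 months could mean events arising since enrollment, or everyone known to have cardiac failure by that date. Without a baseline field the two cannot be reliably separated at analysis, and people with prior failure are eligible.

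At stake is the tolerability half of the primary objective and the hypothesis that outcomes improve safely. The 90-day recurrence comparison is not affected.

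**Working it through.** **1. Objective against analysis.** The finding is one of internal consistency and does not depend on a calculation.

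| Element | Stated aim | Planned handling |
|---|---|---|
| Effectiveness (recurrent CDI) | Compare | Weighted comparison, treated vs controls |
| Utilization, charges, scores, laboratory values | Compare | Weighted comparison |
| Cardiac failure | Part of tolerability, if anything named is | Proportion in the 50 treated only |
| Serious adverse events | Not assigned to an objective | Reported to investigator and IRB; no summary by group |

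**2. Baseline status.** Section 7 plans McNemar's test from baseline to 24 months for discrete outcomes, which requires a baseline value. No cardiac value is listed at Visit 1. Current medications and the open-ended reference to other enrollment data might hint at prior failure, but neither specifies it.

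**3. The plan's own figure.** The documents give no rate, precision or power for cardiac failure. The only power figure is 88%, for recurrence: 26.7% vs 53.8%, 50 treated vs 118 controls, two-sided alpha 0.05. Using the continuity-corrected normal approximation:

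- Pooled proportion = (50 × 0.267 + 118 × 0.538)/168 = 0.457
- SE under the null = √[0.457 × 0.543 × (1/50 + 1/118)] = 0.0841
- SE under the alternative = √[0.267 × 0.733/50 + 0.538 × 0.462/118] = 0.0776
- Correction = ½(1/50 + 1/118) = 0.0142
- z = (0.271 − 0.0142 − 1.96 × 0.0841)/0.0776 = 1.19, so power is 88.2%

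Full enumeration of Fisher's exact test gives 90.0%. The stated 88% is reproduced, but it says nothing about cardiac failure.

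**4. Precision in the treated group.** Exact (Clopper-Pearson) 95% limits with n = 50. For 0 events the upper limit is 1 − 0.025^(1/50) = 7.1%. For x events the limits are the 0.025 quantile of Beta(x, 51 − x) and the 0.975 quantile of Beta(x + 1, 50 − x).

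| Events | Proportion | 95% interval |
|---|---|---|
| 0 | 0% | 0% to 7.1% |
| 2 | 4% | 0.5% to 13.7% |
| 3 | 6% | 1.3% to 16.5% |

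These widths come from the sample size. Neither a comparator nor baseline status would narrow them.

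**5. What a comparison could show.** All rates below are assumptions. Power is for the two-sided Fisher test by full enumeration. The half-width is 1.96 × √[p₁(1 − p₁)/50 + p₀(1 − p₀)/n₀]. The 118 controls are the plan's figure; 50 is an assumed smaller concurrent group, because the documents do not say how many of the 118 are concurrent.

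| Treated vs control | Power, 118 controls | Power, 50 controls | Half-width, 118 controls | Half-width, 50 controls |
|---|---|---|---|---|
| 4% vs 2% | 8% | 0.6% | 6.0 points | 6.7 points |
| 6% vs 2% | 20% | 3% | 7.1 points | 7.6 points |
| 10% vs 2% | 52% | 19% | 8.7 points | 9.2 points |
| 14% vs 2% | 78% | 44% | 9.9 points | 10.4 points |

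With so few events the half-widths are only rough guides.

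**The case against.** The strongest reply is that the plan is less bare than it looks. It never equates tolerability with cardiac failure. It compares ED visits, admissions, blood counts, quality of life and disease activity between groups, and some of these bear on tolerability. Serious events are captured whatever their cause. A reader might therefore infer too much in saying that the trial cannot compare tolerability at all, or that cardiac failure is its only tolerability information. The documents do not support that. What stands is narrower: none of those outcomes is designated a tolerability outcome, utilization is listed without cause, and no adverse-event outcome is compared by group.

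A reader might also infer that a patient with known failure at entry would be counted as an event. No section says so, and the wording can equally mean new events only. What stands is that the plan does not define this and lists no field that would settle it.

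The last objection is that a comparison would add little. Groups form partly by patient choice, events may be very few, weighting on a handful of events is unstable, and power is poor. All of this is right, and it limits the remedy to a descriptive comparison. It does not justify leaving the stated objective without a matching analysis, or leaving the treated-group estimate ambiguous.

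**Conclusion.** The concern holds in this form. Sections 1 and 3 promise a comparison of tolerability, and no adverse-event outcome is compared between groups. Cardiac failure, the one safety event singled out, is estimated in the 50 treated patients only, with baseline status and the meaning of an event left open. This should be corrected. It does not threaten the primary recurrence analysis.

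The wide intervals are not the size of the defect, since they follow from n = 50 and would remain after correction. The gain is an interpretable event definition and a parallel count in untreated patients. At assumed rates of 4% to 6% versus 2%, power is only about 8% to 20% with 118 controls, and lower if fewer are concurrent. Even the corrected analysis cannot establish or exclude a drug effect. The conclusion assumes that no separate data-collection form, outside these documents, already records cardiac status in both groups.

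**What to change.** 1. **Data.** Record history of cardiac failure at Visit 1, and new or worsening failure at Visits 2 to 4 from the health record, with one written definition. Do this in the same way in treated and concurrent untreated patients. State whether the historical controls have these data.
2. **Analysis.** Report new or worsening events by group at 90 days, 12 months and 24 months, with exact 95% intervals and a between-group difference with its interval. Show patients with prior failure separately. Label the comparison descriptive, and make any weighted difference secondary because few events are likely. Give the number of concurrent untreated patients.
3. **If this is not feasible.** Restate the tolerability objective in sections 1 and 3 as descriptive in treated patients only, still with baseline status recorded.

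The cost is a few chart-review fields and one table, with no added visit or test. Because follow-up may be by telephone, completeness of the health record should be reported for each group. The price in interpretation is an imprecise result that must be presented as such. None of this bears on who should be eligible or treated.
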